#### 4.7 Demographic and Other Baseline Characteristics

Descriptive summaries of demographic and baseline characteristics will be presented for the FAS. For categorical summaries, the number and percentage of patients in each category will be presented, and for continuous summaries the n/mean/SD/min/median/max will be presented. Percentages will be based on the number of patients in the FAS. The number of patients with missing values for categorical summaries may be presented if any such values are present in the data.

Summaries of the following characteristics will be presented:

- Sex (male / female)
- Ethnicity (Hispanic or Latino / Not Hispanic or Latino)
- Race (American Indian or Alaska Native / Asian / Black or African American / Native Hawaiian or Other Pacific Islander / White / Multiple) – note that patients who select multiple race groups on the eCRF will be summarized as ‘multiple’
- Age (years) as collected on the eCRF
- Age category in years (<45, ≥45 to <65, ≥65)
- Height (cm)
- Weight (kg)
- Body mass index (BMI) (kg/m^2)
- Indication (DKD / Non-DKD)
- Time since first diagnosis (years)
- Country
- Baseline eGFR (ml/min/1.73m^2)
- Baseline eGFR category (<30, ≥30 to <60, ≥30 to ≤45, ≥45 to <60, ≥60 ml/min/1.73m^2)

- Baseline UACR (mg/g)
- Baseline UACR category (<30, ≥30 to <300, ≥300 mg/g).

Body mass index will be calculated as  $[\text{weight (kg)} / [\text{height (m)}]^2]$ . Time since first diagnosis will be calculated as  $[\text{date of informed consent} - \text{date of first diagnosis} + 1] / 365.25$ .

In the case that the date of first diagnosis of CKD is partial or missing, if only the day is missing then the first day of the month will be imputed. If the month and day are missing, then the first of January will be imputed. If the year or entire date is missing then no imputations will be done, and the patient will not be included in the summary of time since first diagnosis.

Demographic and baseline characteristics will also be listed. Additional to the variables mentioned above, the patient identifier, site, gender identity, childbearing potential (females only), birth year, and additional details of race group for Asians (per eCRF) will be presented.

#### 4.8 Medical History and Baseline Conditions

Patient medical history marked as relevant to study indication (per the eCRF) will be presented for the FAS. The number and percentage of patients with relevant medical history findings will be presented by SOC and PT. Percentages will be based on the number of patients in the FAS.

Patients with multiple medical history findings within the same SOC/PT will be counted once per SOC/PT. The SOCs will be sorted alphabetically, and PTs will be sorted by descending overall frequency (within system organ class). Medical history conditions will be coded using the Medical Dictionary for Regulatory Activities (MedDRA) version 24.0 or higher.

Medical history data will also be listed: the patient identifier, patient population, site, country, SOC, PT and verbatim medical history term, start date/day and end date/day of finding, and an indication of whether finding was ongoing at study start will be presented.

Additionally, a table presenting the number and percentage of patients with baseline conditions as reported on the eCRF will be given by primary SOC and PT for all patients in the FAS. Patients with multiple baseline conditions within the same SOC/PT will be counted once per SOC/PT. The SOCs will be sorted alphabetically, and PTs will be sorted by descending overall frequency (within SOC). Percentages will be based on the number of patients in the FAS. Baseline conditions will be coded using the Medical Dictionary for Regulatory Activities (MedDRA) version 24.0 or higher.

Baseline conditions will also be listed: the patient identifier, patient population, site, country, age, sex, SOC, PT and verbatim term of the baseline condition will be presented.

#### 4.9 Concomitant Medications and Non-Drug Therapies

For the prospective phase, all concomitant medications and non-drug therapies will be collected, and for the retrospective phase only concomitant medications and non-drug therapies that impact the eGFR slope will be collected (e.g. ACEi/ARB/SGLT2i) – note that retrospective concomitant medications and non-drug therapies will be identified as those started before informed consent on the eCRF.

Concomitant medications will be coded according to the most recent available World Health Organization - Drug Dictionary (WHO-DD) version. The number and percentage of patients who took concomitant medications will be summarized by WHO-DD Anatomical Therapeutic Chemical

(ATC) class (ATC3 will be used) and PT for the FAS. Percentages will be based on the number of patients in the FAS. Patients with multiple concomitant medications within the same ATC class and PT will be counted only once per ATC class and PT. The ATC classes will be sorted alphabetically, and PTs will be sorted by descending overall frequency (within ATC class).

Concomitant non-drug therapies will be coded according MedDRA version 24.0 or higher. The number and percentage of patients who took concomitant non-drug therapies will be summarized by SOC and PT for the FAS. Percentages will be based on the number of patients in the FAS. Patients with multiple concomitant non-drug therapies within the same SOC and PT will be counted only once per SOC and PT. The SOCs will be sorted alphabetically, and PTs will be sorted by descending overall frequency (within SOC).

All on-study concomitant medications and non-drug therapies occurring between baseline and the end of study visit (inclusive) will be summarized, including those that started before baseline and continued to be taken on or after baseline. Note that this may include medications and non-drug therapies from both the prospective and retrospective phase. Medications and non-drug therapies that started after informed consent but ended before baseline will not be summarized.

In case of (partially) missing start and end dates of concomitant medications and non-drug therapies, the dates will be imputed so that the extent of exposure to the concomitant medication/non-drug therapy is maximal:

- Missing start day will be imputed as the first day of the month
- Missing end day will be imputed as the last day of the month
- Missing start month will be imputed as the first month of the year (January)
- Missing end month will be imputed as the last month of the year (December).

A listing of all concomitant medications (occurring at any time in either the prospective or retrospective phase) will be presented, including: patient identifier, patient population, age, sex, ATC3 code, PT and verbatim term for the concomitant therapy, start date/day (or 'Before Informed Consent' if the therapy was started before informed consent in which case no start date is recorded), end date/day (or 'Ongoing' if medication is ongoing), all indications for therapy as recorded on eCRF, indication of whether therapy is in the following category [Anti-Hypertensive Treatment, NSAIDs, Anti-Diabetic, Endothelin Receptor Antagonists, Systemic Steroids, Angiotensin Converting Enzyme Inhibitor (ACEi), Angiotensin Receptor Blocker (ARB) and Sodium-Glucose Co-Transporter-2 inhibitors (SGLT2i)], and further for the therapies in this category the dose per administration, dose units, dosing frequency per interval, and route of administration will be presented.

Further, a listing of all concomitant non-drug therapies (occurring at any time in either the prospective or retrospective phase) will be presented including: patient identifier, patient population, age, sex, SOC, PT and verbatim term for the concomitant therapy, start date/day (or 'Before Informed Consent' if the therapy was started before informed consent in which case no start date is recorded), end date/day (or 'Ongoing' if therapy is ongoing), and all indications for therapy as recorded on eCRF.

The listings will present all concomitant medications and non-drug therapies, regardless of when it started/ended. Original (non-imputed) start and end dates will be presented in the listing, and imputed values of the start/end day will not be presented (as day will not be calculable in the case that start/end dates are partial).

## 4.10 Primary Outcome Evaluation

### 4.10.1 Analysis and Data Conventions

This study is exploratory, no formal hypothesis testing will be done.

#### 4.10.1.1 Multi-center Studies

Patients will be recruited from different sites and countries in this study. Since this is an exploratory study, examination of differences in the primary outcome according to site or country are not of high importance, and adjustment of the primary outcome analysis by site/country will not be done. The effects of site/country may be examined as part of the analyses supportive to the primary outcome (see section 4.10.2.2).

#### 4.10.1.2 Handling of Dropouts or Missing Data

Missing data will not be imputed for the primary analysis. Data which will be excluded from the analysis is defined in section 4.10.2.

#### 4.10.1.3 Calculation of eGFR from Serum Creatinine

Serum creatinine measurements will be converted into eGFR measurements according to the Chronic Kidney Disease Epidemiology Collaboration (CKD-EPI) formula, as given in section 5.1.

For retrospective data, if serum creatinine is unavailable but calculated eGFR values are available, then the calculated eGFR values will be used regardless of which formula was used to derive them. The formula used for the derivation will be collected on the eCRF and specified in the listings. If the formula is unknown, then it will be assumed that the CKD-EPI formula (see section 5.1) was used.

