### 3.1.1.1 Study Termination

This study was terminated in July 2022, due to decision of the sponsor. All data available up to the termination will be used in any subsequent analyses and all analyses planned in this SAP (and the corresponding TLF shells) will be performed.

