#### 4.10.2 Primary Outcome Variable

The primary outcome is the homogeneity (eGFR slope shift table) between eGFR slopes derived from retrospective and prospective eGFR values. All analyses of the primary outcome will be done on the FAS, and percentages will be based on the number of patients in the FAS, unless otherwise specified.

Retrospective and prospective eGFR slopes will be derived using a linear random slope model. The prospective eGFR slope for each patient will be derived using eGFR values in the prospective phase as the dependent variable and time in the prospective phase (years, starting from baseline) as the continuous independent variable with random intercept and random slope. The retrospective eGFR slope for each patient will be derived similarly using the data in the retrospective phase, and time in the retrospective phase will be calculated relative to the first retrospective measurement per patient. Note that for the prospective slope, all measurements from baseline until the last available visit will be considered for inclusion in the estimation, including unscheduled visits.

The primary analysis assessing homogeneity between retrospective and prospective eGFR slopes will first be performed using the retrospective eGFR slopes collected from retrospective data, and the prospective eGFR slopes derived using prospective eGFR measurements from Mitra® samples from both at-home and clinic visits. The primary analysis will then be performed again using the retrospective eGFR slopes collected from retrospective data, and prospective eGFR slopes derived from prospective eGFR measurements from venous blood samples from clinic visits. This is in order to assess differences in the slope estimation depending on the data source.

Other than this requirement, all available patient data will be included for the estimation of the retrospective slope. However, for the prospective slope, the following additional data resulting from changes to background therapy will be excluded from the eGFR slope estimation:

- For patients on SGLT2i/ACEi/ARB background therapy at date of eGFR baseline measurement, eGFR data collected after the patient dropped out of SGLT2i/ACEi/ARB will be excluded
- For patients who are not on SGLT2i/ACEi/ARB background therapy at date of eGFR baseline measurement, eGFR data collected after the patient starts SGLT2i/ACEi/ARB will be excluded

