**Equation 1**

$$E(Y_{ij}) = a_0 + b_{0j} + (a_1 + b_{1j})T_{ij}$$

Where  $a_0$  is the fixed effect term for the common intercept (across all patients),  $b_{0j}$  is the term for the random intercept of patient  $j$  and follows a Normal distribution,  $a_1$  is the fixed effect term for the common slope (across all patients) and  $b_{1j}$  is the term for the random slope of patient  $j$  and follows a Normal distribution.  $T_{ij}$  represents the time (in years) in the phase for patient  $j$  and time  $i$ . For a given patient, the random slope quantifies the difference between the observed eGFR slope of the patient and the population-averaged (common) eGFR slope. Therefore the combination of  $a_1 + b_{1j}$  represents the eGFR slope for each patient, and will be the primary quantity of interest in this analysis. The primary analysis will come from an unadjusted model as shown above. An autoregressive covariance structure will be used in this model in the first instance, however other covariance structures may be used, especially in the case of model non-convergence. If an autoregressive covariance structure results in non-convergence, then a compound symmetry structure will be tried. In the case that neither of these covariance structures results in convergence, other structures may be tried and the final choice of covariance structure will be detailed in the output. Note that the eGFR slope resulting from Equation 1 is expected to be negative as eGFR is expected to decline over time.

[figure not shown]
The primary analysis used to evaluate homogeneity of the slopes will be a shift table of the shift in number of patients with categories of estimated eGFR slopes of  $> -1$ ,  $> -3$  to  $-1$  (slow progression) and  $\leq -3$  mL/min/1.73m^2/year (fast progression) from the retrospective phase to the prospective phase. This analysis will be presented overall and for the DKD and non-DKD populations. Percentages will be based on the number of patients within each category in the retrospective phase. This analysis will

[figure not shown]
be performed once using prospective eGFR measurements from Mitra® samples and once using prospective eGFR measurements from venous blood samples.

[figure not shown]

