Summary statistics (mean, SD, min, median, max) of the estimated eGFR slopes will be presented by phase, for the overall population and for the DKD and non-DKD populations, and this analysis will be performed once using prospective eGFR measurements from Mitra® samples and once using prospective eGFR measurements from venous blood samples.

To aid in assessing the reliability of the slope estimation, the residual variance (i.e. mean squared error) of the slope estimates will also be presented for both the retrospective and prospective slopes, and this residual variance will be estimated from the linear random slope model in [Equation 1](#).

A by-patient listing of the primary outcome data will be provided including patient identifier, site, country, age, sex, race, patient population (DKD/non-DKD), phase of measurement (retrospective/prospective), visit, date of baseline, sample collection/assessment day, indicator of whether sample was taken and reason not done (for prospective eGFR only), name of formula used to calculate eGFR, eGFR measurement, and indication of whether paper diary was reviewed (at clinic visits in prospective phase only), and data source (Mitra®/venous blood) for prospective phase. Note that the assessment day will be calculated relative to baseline. Data from all visits (including unscheduled visits) will be listed, and data collected 4 weeks before AKI and up to 8 weeks after the AKI (which were excluded from the analysis) will be listed and marked with [AKI] in the listing. Data excluded from the primary analysis due to changes in background therapy will be marked with [BAC] in the listing.

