## 5 Appendix

### 5.1 GFR CKD-EPI Formula

Calculation Name		GFR CKD-EPI	
Formula	Units	Decimal Places	

Conventional:
 
Black or African American formulas:
 
Female with a serum creatinine value of <math>\leq 0.7</math> mg/dL  <math>166 \times (\text{Serum Creatinine (mg/dL)} / 0.7)^{-0.329} \times (0.993)^{\text{age}}</math>
 
Female with a serum creatinine value of <math>> 0.7</math> mg/dL  <math>166 \times (\text{Serum Creatinine (mg/dL)} / 0.7)^{-1.209} \times (0.993)^{\text{age}}</math>
 
Male with a serum creatinine value of <math>\leq 0.9</math> mg/dL  <math>163 \times (\text{Serum Creatinine (mg/dL)} / 0.9)^{-0.411} \times (0.993)^{\text{age}}</math>
 
Male with a serum creatinine value of <math>> 0.9</math> mg/dL  <math>163 \times (\text{Serum Creatinine (mg/dL)} / 0.9)^{-1.209} \times (0.993)^{\text{age}}</math>
 
White, American Indian, Alaska Native, Asian, Native Hawaiian, Other Pacific Islander, Other formulas:
 
Female with a serum creatinine value of <math>\leq 0.7</math> mg/dL  <math>144 \times (\text{Serum Creatinine (mg/dL)} / 0.7)^{-0.329} \times (0.993)^{\text{age}}</math>
 
Female with a serum creatinine value of <math>> 0.7</math> mg/dL  <math>144 \times (\text{Serum Creatinine (mg/dL)} / 0.7)^{-1.209} \times (0.993)^{\text{age}}</math>
 
Male with a serum creatinine value of <math>\leq 0.9</math> mg/dL  <math>141 \times (\text{Serum Creatinine (mg/dL)} / 0.9)^{-0.411} \times (0.993)^{\text{age}}</math>
 
Male with a serum creatinine value of <math>> 0.9</math> mg/dL  <math>141 \times (\text{Serum Creatinine (mg/dL)} / 0.9)^{-1.209} \times (0.993)^{\text{age}}</math>
 
Creatinine in mg/dL is rounded to 2 decimal places prior to applying the formula.
	mL/min/ 1.73m 	0	

SI:
 
Serum creatinine in <math>\mu\text{mol/L}</math> will be rounded to zero decimal place and converted to mg/dL by multiplying by 0.01131. This creatinine value in mg/dL will be rounded to 2 decimal places. This creatinine result will be used in the GFR Conventional formulas listed above.
	mL/min/ 1.73m 	0	
Limitations/Special Notes:	Age is truncated to a whole number prior to performing the calculation.		

Note that if a patient selects multiple races on the eCRF, the CKD-EPI formula for ‘Other’, should be applied.

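### Retrospective values recorded only as eGFR enter the primary slope under whatever formula produced them, although many could be converted to the SAP Section 5.1 formula

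*SAP*

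**What the plan says.** SAP 4.10.1.3 converts serum creatinine to eGFR with the CKD-EPI formula of SAP 5.1. For retrospective data without creatinine but with a recorded eGFR, "then the calculated eGFR values will be used regardless of which formula was used to derive them". It adds that "The formula used for the derivation will be collected on the eCRF and specified in the listings", and "If the formula is unknown, then it will be assumed that the CKD-EPI formula" of Section 5.1 was used.

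SAP 4.10.2 then states that "all available patient data will be included for the estimation of the retrospective slope", as Protocol 7.2.1 also does. On Equation 1 it says "The primary analysis will come from an unadjusted model as shown above"; the equation has a common and a patient-level intercept and slope, and no term for the formula. After collection, the only visible use of the formula is a column in the by-patient listing ("name of formula used to calculate eGFR"), next to age, sex and race.

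Protocol 3.3.2, criterion 9, requires at least 4 serum creatinine values, with 1 to 5 years between oldest and newest. The study was terminated in July 2022, but under SAP 3.1.1.1 "all analyses planned in this SAP (and the corresponding TLF shells) will be performed", so the rule still applies.

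**The concern.** Criterion 9 means that an eGFR-only value in an eligible patient supplements at least 4 values computed with Section 5.1. If its formula gives systematically higher or lower results, the record contains a step that has nothing to do with the kidney. A random-slope model without a formula term fits part of that step as decline or improvement. How much depends on position: a value near either end pulls the slope, and one in the middle hardly moves it.

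Prospective serum values all use Section 5.1, so the distortion falls on the retrospective side of the shift table only. That table is the primary analysis. A patient moved across -3 or -1 mL/min/1.73m² per year can appear as heterogeneity between the phases, or hide it, because of how a laboratory reported eGFR. Protocol 1.3 itself warns that differences between laboratories can affect past eGFR and slopes. For a known, creatinine-based formula this part of the problem is avoidable.

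**Working it through.** The plan gives no figure on this point to reproduce. The check is a calculation on assumed inputs.

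**Inputs from the documents.** Cut-offs -1 and -3 (SAP 4.10.2); at least 4 creatinine values over 1 to 5 years (criterion 9); random intercept and slope (Equation 1); Section 5.1 formula and rounding.

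**Assumptions.** Mean intercept 50 (SD 14), mean slope -3.5 (SD 2.5), independent residuals with SD 4, variances treated as known, 400,000 simulated patients. The SAP instead estimates variances by REML and tries an autoregressive structure first. Formula differences of 5, 10 and 15% at eGFR 50 are steps of 2.5, 5 and 7.5, in either direction.

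**Slope bias.** The predicted slope is a weighted sum of the patient's values, so bias = step × w, where w is the total weight on the eGFR-only values. For two values after the last creatinine, w = 0.202, giving 2.5 × 0.202 = 0.51 to 7.5 × 0.202 = 1.52 mL/min/1.73m² per year.

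**Misclassification.** Percentage of affected patients whose estimated category differs from the true one. Creatinine is at 0, 1, 2 and 3 years except in the last row (0, 0.67, 1.33 and 2 years). Ranges cover both directions. Converted values carry a rounding error of SD 0.55.

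| eGFR-only values at | w | Converted | Kept, 5% | Kept, 10% | Kept, 15% | Left out | Kept minus converted |
|---|---|---|---|---|---|---|---|
| 0.5 y | -0.092 | 27.5 | 27.6-28.0 | 28.3-29.3 | 29.5-31.4 | 28.7 | 0.1-3.9 |
| 1.5 y (mid-record) | 0.003 | 28.7 | 28.7 | 28.6-28.7 | 28.6-28.7 | 28.7 | about 0 |
| 2.5 y | 0.096 | 27.3 | 27.5-27.9 | 28.3-29.3 | 29.6-31.6 | 28.8 | 0.2-4.3 |
| 3.25 y | 0.139 | 25.1 | 25.8-26.1 | 27.9-29.3 | 30.6-34.2 | 28.7 | 0.7-9.1 |
| 3.25 and 3.45 y | 0.202 | 23.1 | 24.8-25.4 | 29.0-32.2 | 33.7-42.0 | 28.8 | 1.7-18.9 |
| 2-year span, 2.25 and 2.45 y | 0.249 | 29.3 | 30.7-32.3 | 34.4-40.4 | 38.0-51.6 | 35.6 | 1.4-22.3 |

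**Share of the table.** If 5-30% of patients had such values (assumption), 3-year records give from 0.1 × 0.05, practically 0, to 18.9 × 0.30 = 5.7%. At a 5% difference the maximum is (25.4 - 23.1) × 0.30 = 0.7%, or (32.3 - 29.3) × 0.30 = 0.9% for the 2-year span. The 2-year pair at 15% would reach 22.3 × 0.30 = 6.7%.

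**Sensitivity to assumptions.** Over nine settings (residual SD 3-5, slope SD 1.5-3.5; 3-year record, two late values), misclassification is 15-28% converted, 20-33% left out, and 18-29 / 24-36 / 30-52% kept at 5 / 10 / 15%. Conversion is lowest in all nine.

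**Feasibility.** Section 5.1 says "Creatinine in mg/dL is rounded to 2 decimal places prior to applying the formula" and reports whole numbers. Example: male, age 60, coefficient 141, recorded eGFR 55 from a formula assumed to run 10% high. Then 55/1.10 = 50 and 141 × 0.993^60 = 92.5. Recovered creatinine is 0.9 × (50/92.5)^(-1/1.209) = 1.497, rounded to 1.50. Recomputed eGFR is 92.5 × (1.50/0.9)^(-1.209) = 49.9, reported as 50. Over eGFR 20-85 and factors 0.85-1.15, the rounding error has SD about 0.4-0.6. It changes the category in about 1-2% of affected patients.

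**The case against.** The other side has substance. Every driver of size is assumed, and the share of eGFR-only values could be close to zero: criterion 9 and the CRF list in Protocol 3.1 are built around serum creatinine, so the rule is a fallback for supplementary values. Even fully converted early or late records misclassify 23-28% over three years, so ordinary slope noise is usually the larger problem. The study is exploratory. Conversion needs published equations for the other formulas, and the eCRF is not among the documents, so it is unknown whether it records the formula version or the race term applied. All of this stands and lowers the priority. None of it makes keeping the values better than converting those that can be converted.

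Some stronger readings are tempting but not supported:

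- *Up to about 14% of the table is wrong.* Counting every category change against a record without a step gives 6-46% of affected patients in 3-year early or late records, or 0.3-14% of the table. About 25-45% of those changes move towards the true category. The net figures above are the relevant ones.
- *No sensitivity analysis is planned.* Supportive section 4.10.2.2 is not visible. Nor is the AKI exclusion rule that the listing text presupposes. A check may exist there.
- *The rule contradicts the protocol.* Protocol 3.1 speaks of slopes from creatinine values, but also collects all available historical eGFR values, and Protocol 7.2.1 uses all available data.
- *Taking an unknown formula as CKD-EPI distorts the slope or conceals values.* It changes no number, and the SAP does not say that the listing overwrites an unknown formula.
- *eGFR-only values should be dropped.* For two late values in a 3-year record, leaving them out (28.8%) is worse than keeping them at a 5% difference (24.8-25.4%) and about even or slightly better at 10% (29.0-32.2%).

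**Conclusion.** The point holds as an avoidable source of bias on one side of the primary shift table. In 3-year records with assumed formula differences of 5-15% at eGFR 50, keeping instead of converting adds, among affected patients only, about 0-4 percentage points of misclassification for one early value, 1-9 for one value after the last creatinine, 2-19 for two such values, and practically none mid-record. With an assumed 5-30% of patients affected, this is roughly 0-6% of the table, and at most about 1% at a 5% difference.

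These sizes rest on the assumed variances, value positions and formula differences; the documents supply none of them. They do not show that the primary result is unreliable. Priority is low to moderate, depending on how many eGFR-only values exist.

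**What to change.** In SAP 4.10.1.3:

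1. Where the recorded formula is known, creatinine-based and invertible from recorded inputs, recover creatinine and recompute eGFR with Section 5.1 before fitting the primary retrospective slope.
2. Keep unknown or non-convertible values in the primary slope as reported, in line with Protocol 7.2.1, and list them as unknown or not convertible.
3. Report the numbers of patients and values that were converted, unknown and not convertible. If any were not converted, and no such analysis already exists in the sections not visible, repeat the shift table without them, for both the Mitra and the venous version.

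The cost is some derivation work, reliance on published equations for the other formulas, and at most one more retrospective model run with its tables. Converted values carry a small rounding error (SD about 0.4-0.6 mL/min/1.73m²). Precision is lower in the sensitivity table only, and no data leave the primary slope. The change removes formula differences only; differences between laboratories in measuring creatinine remain.
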